### 12.1. Early Termination Monitoring Visit

[figure not shown]
If early termination of the study is required, each site will undergo a monitoring visit as described in the monitoring plan to conclude any outstanding issues, collect all outstanding CRF information, verify device accountability, and discuss any other items relevant to the conclusion of the study. Subjects will be notified of the termination of the study. Any enrolled subjects will continue to be followed per the study protocol requirements until a study closeout plan is implemented that outlines alternative follow-up procedures.

[figure not shown]

[figure not shown]

[figure not shown]

[figure not shown]

[figure not shown]

[figure not shown]

[figure not shown]

[figure not shown]

[figure not shown]

## **14. Ethics and Protection of Human Subjects**

### **14.1. Ethical Standard**

As the Sponsor of this study, Biosense Webster has the overall responsibility for the conduct of the study, including assurance that the study meets the regulatory requirements of the Food and Drug Administration and the MDD 93/42/EC and the local government. The Sponsor will also maintain compliance with Good Clinical Practice (ICH version 6, revision 2, 11 June 2015), the European standard EN ISO 14155 (Clinical Investigation of Medical Devices for Human Subjects), the Declaration of Helsinki (Ethical Principles for Medical Research Involving Human Subjects, Brazil, October 2013), Sponsor general duties (21 CFR 812.40), selection of investigators (21 CFR 812.43), monitoring (21 CFR 812.46), supplemental applications (21 CFR 812.35 [a] and [b]),

maintaining records (21 CFR 812.140 [b]), and submitting reports (21 CFR 812.150 [b])), and to local regulations where required.

- **General Duties**  
Biosense Webster's general duties consist of submitting the IDE application to appropriate regulatory agencies, assuring that sites have received IRB/EC approvals prior to shipping the devices, selecting investigators, ensuring proper clinical site monitoring and verifying that subject informed consent is obtained.
- **Data Quality and Reporting**  
Biosense Webster is responsible for providing quality data that satisfy federal regulations and informing proper authorities of serious unanticipated adverse events and deviations from the protocol.
- **Selection of Investigators**  
Potential investigational sites will undergo an evaluation to ensure that the site has the appropriate facilities and personnel to conduct the study in compliance with the clinical investigational plan. Based on outcome of evaluation process, Biosense Webster will select qualified investigators, ship devices only to participating investigators, obtain a signed Investigator's Agreement and provide the investigators with the information necessary to conduct the study.
- **Supplemental Applications**  
As appropriate, Biosense Webster will submit changes in the Clinical Investigation Plan to the investigators to obtain applicable re-approvals from IRBs/ECs.
- **Maintaining Records**  
Biosense Webster will maintain copies of correspondence, data, adverse device effects and other records related to the study. Biosense Webster will maintain records related to the signed Investigator Agreements.
- **Submitting Reports**  
Biosense Webster will submit any required regulatory reports identified in this section of the regulation. This includes unanticipated adverse device effects, withdrawal of IRB/EC approval, current investigators list, annual progress reports, recall information, final reports and protocol deviations.

#### **14.2. Institutional Review Board/Ethics Committee**

The investigator will obtain written and dated approval from the responsible IRB/EC for the study protocol (or amendment[s]) and informed consent before enrolling study subjects. Biosense Webster and the IRB/EC must approve in writing any changes to the protocol that affect the rights safety and/or welfare of the subjects or may adversely affect the validity of the study.

A copy of the IRB/EC approval letter addressed to the investigator must be sent to Biosense Webster certifying study approval prior to subject enrollment. Investigators are responsible for submitting and obtaining initial and continuing review (per local requirements) of the study by their IRB/EC.

### **14.3. Informed Consent Process**

#### **14.3.1. Consent/Assent and Other Informational Documents Provided to Subjects**

Patient informed consent must be obtained and documented according to the principles of informed consent in the latest version of the Declaration of Helsinki (Brazil, 2013), ISO 14155, using the document approved by the reviewing IRB/EC. Informed consent is mandatory and must be obtained from all subjects prior to their participation in the study.

#### **14.3.2. Consent Procedure and Documentation**

Informed consent is a process that is initiated prior to the individual's agreeing to participate in the study and continues throughout the individual's study participation. Discussion of risks and possible benefits of participation will be provided to the patients as part of the informed consent process. Consent forms will be IRB/EC-approved and the patient will be asked to read and review the document. The investigator, or designee, will explain the research study to the patient and answer any questions that may arise. All patients will receive a verbal explanation in terms suited to their comprehension of the purposes, procedures, and potential risks of the study and of their rights as research subjects. Information should be given to the patient in a language and at a level of complexity understandable to the patient in both oral and written form by the principal investigator or designee. Patients will have ample opportunity to review the written consent form and to ask questions prior to signing.

Prior to participation in the trial, the Patient ICF should be signed and personally dated by the patient or his/her legal representative. If a witness is used for an illiterate or compromised patient, the witness should also sign the consent form, attesting that informed consent was freely given by the patient or his/her legal representative. The patients may withdraw consent at any time throughout the course of the trial. The rights and welfare of the patient will be protected by emphasizing to them that the quality of their medical care will not be adversely affected if they decline to participate in this study. A signed and dated copy of the Patient ICF must be collected from each enrolled subject and kept in the study subject files and medical records. The site should provide each subject with a copy of their fully executed ICF.

Biosense Webster, Competent Authority (where applicable), and the reviewing IRB/EC must approve any modifications to the Patient ICF for this clinical investigation. A copy of the IRB/EC approved Patient ICF must be maintained by each investigator.

Documentation of the consent process for each subject should be maintained by each investigator.

Patients should not be coerced, persuaded, or unduly influenced to participate or continue to participate in the trial.

### **14.4. Subject and Data Confidentiality**

During this clinical investigation, representatives of the Sponsor will comply with in-country privacy laws and regulations regarding contact with subjects, their medical record information, copying of information, and protection of the subject identities.

All information and data sent to Biosense Webster concerning subjects or their participation in this clinical investigation will be considered confidential. Only authorized Biosense Webster personnel or representatives (including contracted service providers,

i.e. Core Lab, Clinical Research Associate, CRO, etc.) and/or representatives of the FDA or Competent Authorities acting in their official capacities will have access to these confidential files upon request (including, but not limited to, laboratory test result reports, ECG reports, admissions/discharge summaries for hospital admission occurring during a subjects study participation and autopsy reports for deaths occurring during the clinical investigation). Some of the countries to which the study subjects and investigators personal data may be transferred may not offer as comprehensive a level of protection of personal data as within the European Union but Sponsor will put adequate measures in place to act in compliance with regional policies and requirements and to ensure a sufficient level of data protection. All data used in the analysis and reporting of this evaluation will exclude identifiable reference to the subject.

#### **14.4.1. Research use of Stored Data**

- Intended Use: Data collected under this protocol may be used to study Atrial Fibrillation.
- Storage: Access to stored data will be limited. Data will be stored using codes assigned by the sponsor. Data will be kept in password-protected computers. Only investigators and the sponsor will have access to the data.

### **15. Source Documents and Access to Source Data/Documents**

Data entered on to the eCRFs will be taken from source documentation, such as hospital procedure reports, admission and discharge summaries, other hospital or investigator office/clinic documents, and system data (CARTO®, generator). If unique study parameters are not documented on standard hospital or office reports, a worksheet may be developed to record this information. The worksheet shall be signed by the PI or authorized designee and will serve as the basis for monitoring the eCRFs. Electronic subject records will be considered as source documents. A print-out of a completed eCRF cannot be used as source documentation.

Investigators should maintain information in the subject's medical records, which corroborate data collected on the eCRFs. In order to comply with these regulatory requirements, at minimum, the following is a list of information that should be maintained.

- Medical history/physical condition of the study subject before involvement in the study sufficient to verify protocol selection criteria (if not already present).
- Dated and signed notes from the day of entry into the study including the study Sponsor (Biosense Webster), protocol number, clinical site, subject number assigned and a statement that consent to participate in the study was obtained.
- Dated and signed notes from each study visit with reference to the eCRFs for further information, if appropriate (for specific results of procedures and exams).
- Reports on AEs and their resolution, including supporting documents such as discharge summaries, EP lab reports, ECGs, lab results.
- Notes regarding protocol-required medication and prescription medications taken during the study (including start and stop dates).
- Notes on subject's condition upon completion of or withdrawal from the study.

Only authorized Biosense Webster personnel or representatives, authorized site personnel, local government authorities, or the FDA, acting in their official capacities, will have access to these confidential files.

## **16. Quality Assurance and Quality Control**

QC procedures will be implemented beginning with the data entry system and ongoing QC checks will be run on the database. Any missing data or data anomalies will be communicated to the site(s) for clarification/resolution.

Following written SOPs, monitors will verify that the clinical trial is conducted and data are generated, documented, and reported in compliance with the protocol, GCP, and the applicable regulatory requirements. If noncompliance is identified, Sponsor is required by regulation to implement measures to secure compliance.

The investigational site will provide direct access to all trial related sites, source data/documents, and reports for the purpose of monitoring and auditing by the sponsor, and inspection by local and regulatory authorities.

## **17. Data Handling and Record Keeping**

### **17.1. Data Collection and Management Responsibilities**

The Sponsor will be responsible for all data management activities. These activities include development of an electronic data collection (EDC) system and utilizing a validated EDC system into which all study data will be entered. The Sponsor will be responsible for reviewing all data to ensure the overall integrity of the database.

#### **17.1.1. Data Collection**

Electronic Case Report Forms (eCRFs) will be used to collect all subject data during this clinical investigation. eCRFs have been developed to capture the information outlined in this clinical investigation Plan. Modification to the eCRF will only be made if deemed necessary by the sponsor. Data on these eCRFs will be monitored (source verified) and the monitor will ask the site representative to correct if necessary to match the source documents. Changes made to the data will be tracked in the electronic audit trail. The investigator will be required to sign designated eCRFs as verification that they have been reviewed and the data entered are correct. Data from these eCRFs will be sent to the Sponsor, and/or 3rd party affiliate acting on behalf of the Sponsor, and used in the analysis of clinical investigation results.

At the completion of the study ablation procedure, two back-up copies of the CARTO® and generator log files will be made. One copy should be kept at the site within the investigator site or subject binders, and one fully anonymized copy will be provided to / collected by the Sponsor.

If performed and recorded, a copy of the fully anonymized angiography images (preferably with contrast), confirming position of the balloon and occlusion of the PVs will be provided to / collected by the Sponsor.

#### **17.1.2. Data Reporting**

The investigator, or a designated individual, is responsible for ensuring that clinical investigation data are properly recorded on each subject's eCRF and related documents. Completed eCRF will be reviewed and monitored by the sponsor personnel, or an appropriately qualified and trained designee, throughout the clinical investigation. To this end, the Investigator and institution must permit inspection of the trial files and subject eCRFs by such representatives and/or responsible government agencies.

Investigators are required to prepare and submit accurate and timely reports on this study to the governing IRB/EC and/or Biosense Webster.

**Table 17.1.2A. Responsibilities for Preparing and Submitting Reports**

Type of Report	Prepared by Investigator For	Time of Notification
Subject withdrawal	Biosense Webster	Should report within 5 working days
Withdrawal of IRB/EC approval	Biosense Webster	Should report within 5 working days
Final report	Biosense Webster, IRB/EC	Will prepare a final report for the clinical investigation as required per national regulations.
Informed consent not obtained from subject	Biosense Webster, IRB/EC (per IRB/EC requirements)	Should report within 5 working days

It is recommended that all eCRF data be entered by the designated site personnel as soon as possible. For AE reporting, refer to the Adverse Event Reporting Requirements and timelines noted within this clinical investigation protocol (section 9.5).

### 17.1.3. Data Verification and Review

Biosense Webster will track the amount of missing data and contact sites as appropriate to instruct them on steps to minimize missing data and remain compliant with protocol required assessments. Missing or unclear data will be queried as necessary throughout the trial. Biosense Webster will request further documentation such as physician and/or cardiac EP lab procedure notes when complications or device deficiencies are observed and reported. Biosense Webster will be responsible for auditing the database and confirming the overall integrity of the data.

### 17.1.4. Final Data Analysis

All exported datasets for analyses will undergo a final data review before final database lock. Once all critical data are monitored and locked, the final analyses of clinical investigation data will be performed.

## 17.2. Study Record Retention and Archiving

Records and reports for the study will remain on file at the site for a minimum of 2 years or per country specific record retention requirements following notification by the sponsor that all investigations have been terminated or completed. This documentation must be accessible upon request by the regulatory authorities, the sponsor, or a designee. The sponsor must approve archiving, transfer, and destruction of the documentation, in writing, prior to the actual archiving, transfer, and destruction. The investigator must notify the sponsor, in writing, of transfer location, duration, and the procedure for accessing the study documentation.

If the investigator retires, relocates, or withdraws from assuming primary responsibility for keeping the study records, custody transfer per written notice must be submitted to the sponsor indicating the name and address of the person accepting primary responsibility. The IRB/EC must be notified in writing of the name and address of the new custodian. Record retention dates must be provided to all parties by the sponsor's corporation.

## 18. Study Suspension or Termination

This study may be temporarily suspended or prematurely terminated at the discretion of the Sponsor. The Sponsor may also terminate a site prior to study completion if the Sponsor believes the site is no longer capable of participating (e.g., cannot fulfill subject enrollment or protocol compliance goals, site suspension by IRB/EC). If the study is prematurely terminated or suspended, the PI will promptly inform the IRB/EC and will provide the reason(s) for the termination or suspension.

If suspension or premature termination occurs, the terminating party shall justify its decision in writing and promptly inform the other parties with whom they are in direct communication. The principal investigator and sponsor shall keep each other informed of any communication received from either the IRB/EC or the regulatory authority.

If early termination of the study is required due to safety concerns or the occurrence of unanticipated adverse or device events, each site will undergo a monitoring visit to conclude any outstanding issues, collect all outstanding CRF information, verify device accountability, and discuss any other items relevant to the conclusion of the study. Any enrolled subjects will continue to be followed per the study protocol requirements.

If, for any reason, the sponsor suspends or prematurely terminates the study at an individual study site, the sponsor shall inform the responsible regulatory authority as appropriate and ensure that the IRB/EC is notified, either by the principal investigator or by the sponsor. If the suspension or premature termination was in the interest of safety, the sponsor shall inform all other principal investigators.

Circumstances that may warrant termination or suspension include, but are not limited to:

- Determination of unexpected, significant, or unacceptable risk to subjects
- Demonstration of efficacy that would warrant stopping
- Insufficient compliance to protocol requirements
- Data that are not sufficiently complete and/or evaluable
- Determination of futility

Study may resume once concerns about safety, protocol compliance, data quality are addressed and satisfy the sponsor, IRB/EC and/or regulatory agency.

## 19. Data and Publication Policy

Publications and/or presentation of clinical investigation results will be coordinated between Biosense Webster, Inc. and the clinical investigation author(s). Authorship will be determined prior to development of any manuscript. All information concerning the study, investigational medical device, sponsor operations, patent application, manufacturing processes, and basic scientific data supplied by the sponsor to the investigator and not previously published, are considered confidential and remain the sole property of the sponsor.

## 20. Document Filing

A copy of all approved versions of the Investigation Protocol will be kept by the site in the Investigator Site File and will be kept by the sponsor in the Sponsor Trial Master File.

1 STUDY DESIGN

This clinical investigation is a prospective, multicenter, single arm clinical evaluation utilizing the Biosense Webster HELIOSTAR™ catheter, in conjunction with the LassoStar™ catheter and Multi-Channel RF Generator, for the treatment of drug refractory symptomatic paroxysmal atrial fibrillation (PAF) with pre-specified performance goals for safety and effectiveness.

An adaptive Bayesian design will be used to determine the sample size. Up to a maximum of 400 evaluable subjects with symptomatic PAF may be enrolled in the main study phase.

To minimize the learning curve effect on the evaluation of safety and effectiveness of the HELIOSTAR™ catheter, a maximum of 240 roll-in subjects will be enrolled in the study. One (1) to three (3) roll-in subjects will be prospectively assigned to each ablating physician per the physician training charter. These subjects will not be counted towards the enrollment cap of 400 evaluable subjects. All subjects will be evaluated at 7 days, 1, 3, 6 and 12 months following the index procedure. Data for roll-in subjects will be analyzed separately from the main phase.

A focused neurological evaluation will be integrated within the Main Study. Forty (40) subjects enrolled in the main study will be included in the Neurological Assessment Evaluable (NAE) subset. NAE subjects will be assessed for incidence of post-ablation symptomatic and asymptomatic cerebral emboli.

Forty (40) subjects enrolled in the main study will be included in the CT/MRA subset. Subjects in the CT/MRA subset will undergo the CT/MRA exams at baseline and 3 months post ablation procedures for the assessment of PV stenosis. A subject may be permitted to participate in both the NAE and CT/MRA assessments.

2 TREATMENT ASSIGNMENT

This is a single-arm study. All subjects will be treated with the HELIOSTAR™ catheter.

3 RANDOMIZATION AND BLINDING PROCEDURES

[figure not shown]
This study is a non-randomized single-arm study. Therefore, masking of treatment assignment for operators and subjects will not be performed.

[figure not shown]
This study will employ several measures to minimize operational bias.

[figure not shown]
- Screening logs will be maintained at sites to confirm consecutive eligible subjects are considered for participation in the study
- Timing of the interim analyses for sample size selection will not be revealed to sites
- An independent statistician will be responsible for performing interim analyses

[figure not shown]
Biosense Webster, Inc

[figure not shown]
- Results from the interim analyses will not be shared with the Sponsor or sites unless the interim analysis results in a decision to stop enrollment or to file for approval
- Sponsor personnel directly involved in the conduct of the study will not have access to intermediate aggregated summaries of primary or secondary safety and effectiveness endpoint data until preparation for filing for approval

[figure not shown]

[figure not shown]

[figure not shown]

[figure not shown]

[figure not shown]

[figure not shown]

[figure not shown]

[figure not shown]

[figure not shown]

[figure not shown]

[figure not shown]

[figure not shown]

[figure not shown]

[figure not shown]

[figure not shown]

[figure not shown]

[figure not shown]

[figure not shown]

[figure not shown]

Biosense Webster, Inc

[figure not shown]

[figure not shown]

[figure not shown]

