- 12 Month Single Procedure Treatment Success: Defined as acute procedural success and freedom from documented symptomatic AF/AT/AFL (of unknown origin) episodes based on electrocardiographic data ( $\geq 30$  seconds on arrhythmia monitoring device) through the effectiveness evaluation period. Repeat ablation or surgical treatment for AF at any time, DC Cardioversion during the effectiveness evaluation period, Continuous AF/AT/ AFL (except CTI dependent) on a standard 12-lead ECG during the effectiveness evaluation period, class I and/or III AAD usage at any time beyond the 3-month follow-up visit window (i.e., at any time from day 105 to 365 post index procedure), oral Amiodarone usage after the index procedure, or failure to use the HELIOSTAR™ catheter for isolation of clinically relevant PVs (all PVs except those that are silent and/or cannot be cannulated) in the index procedure constitutes treatment failure.

**Population:** Patients undergoing catheter ablation for the treatment of drug refractory symptomatic PAF.

**Phase:** Pivotal

**Clinical Sites:** Up to 40 clinical sites in the United States (US) and outside the United States (OUS).

**Study Duration:** The study duration is anticipated to be approximately 3.5 years; 2.5 years for the enrollment phase and an additional 1 year to complete follow-up.

**Subject Study Duration:** Enrolled subjects who undergo the ablation procedure with the investigational device will be followed for 12 months post index procedure.

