#### 9.6. Safety Oversight

Safety oversight will be conducted as described in the safety management plan. Aggregate safety data will be reviewed regularly throughout the course of the study by the study safety lead or designee to promptly identify new issues or trends which may have an impact on the conduct of the study and/or subject safety. Under the rules of an approved study-specific charter, safety data will also be reviewed by an established DMC which may recommend appropriate action(s) to ensure subject safety. A Clinical Events Committee (CEC) will be implemented to adjudicate the primary safety endpoint events. The CEC will operate as described in the CEC Charter.

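### SAP section 3 permits interim results to reach the sponsor and sites once enrolment stops, with up to a year of primary effectiveness follow-up still open

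*SAP*

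**What the plan says.** SAP section 1 sets the design: "An adaptive Bayesian design will be used to determine the sample size", with a cap: "Up to a maximum of 400 evaluable subjects with symptomatic PAF may be enrolled in the main study phase". SAP section 3 states that operators and subjects are not masked and lists measures against operational bias. Four of them matter here:

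- Sites are not told when the interim analyses take place.
- "An independent statistician will be responsible for performing interim analyses".
- "Results from the interim analyses will not be shared with the Sponsor or sites unless the interim analysis results in a decision to stop enrollment". The sentence goes on to name a decision to file as an alternative trigger.
- Sponsor staff with a direct part in running the trial "will not have access to intermediate aggregated summaries of primary or secondary safety and effectiveness endpoint data until preparation for filing for approval".

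The Protocol Summary (Study Duration) plans "2.5 years for the enrollment phase and an additional 1 year to complete follow-up". The primary effectiveness endpoint is judged over day 91-365. Besides documented recurrence, a subject fails through cardioversion or repeat ablation in that window, through a Class I or III antiarrhythmic for atrial arrhythmia beyond the 3-month visit window, or through oral amiodarone at any time after the index procedure. Protocol 8.5 leaves repeat procedures to the investigator's discretion.

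Protocol 9.6 adds: "Aggregate safety data will be reviewed regularly throughout the course of the study by the study safety lead or designee", alongside a data monitoring committee and a clinical events committee.

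**The concern.** The interim analyses decide when to stop enrolling. At a stop, the subjects enrolled most recently have most or all of their evaluation window ahead of them, and they will enter the final analysis. Yet that is the moment at which the bar on sharing lifts, and sites are named among the possible recipients. Nothing in the visible text limits what is shared to the decision itself.

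Several failure criteria are acts of an unmasked clinician. A site that has seen interim estimates could, without any bad faith, become slower or quicker to cardiovert, re-ablate or prescribe in subjects still being followed. There is no control arm in which the same shift would cancel, so any change moves the estimate directly against the performance goal. The SAP already treats site knowledge as a risk, since it hides even the timing of the interims from sites. Allowing the results to reach them while outcomes are open works against that aim.

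**Working it through.** **1. Timeline.** The plan's own duration reproduces: 2.5 years of enrolment + 1 year of follow-up = 3.5 years. The last subject enrolled reaches day 365 one year after enrolment stops, and the 12-month visit window runs to day 405. So up to a year of primary effectiveness follow-up is open when the bar lifts.

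**2. The two measures side by side.**

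| | Interim results | Intermediate endpoint summaries |
|---|---|---|
| Who is kept out | Sponsor and sites | Sponsor personnel directly involved in conduct |
| Until when | A decision to stop enrolment, or a decision to file | Preparation for filing |
| Sites covered after an enrolment stop? | No | Not mentioned |

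For sponsor conduct staff there are two release times, and the text does not say which governs. For sites, no visible rule applies after an enrolment stop.

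**3. Subjects still open at an early stop (illustration).** The inputs are 400 subjects (SAP section 1) and 30 months (2.5 years, Protocol Summary). Even main-study accrual is an assumption, as are the stopping sizes, because the visible text gives neither the interim schedule nor the thresholds.

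- Pace: 400 / 30 = 13.3 per month.
- Enrolled in the last 12 months: 13.3 × 12 = 160.
- Stop at 300: 160 / 300 = 53%.
- Stop at 200: 160 / 200 = 80%.
- Still inside the 90-day blanking period: 160 × 90 / 365.25 = about 39 subjects, whose whole evaluation window lies ahead.

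**4. Sensitivity to pace.** Roll-in subjects are treated first, so the main study may accrue in less than 30 months. Over 2.0 years the pace is 400 / 2.0 = 200 per year, and over 1.5 years it is 400 / 1.5 = 267 per year. At a stop at 300, the share short of day 365 becomes 200 / 300 = 67% or 267 / 300 = 89%.

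**5. What the count means.** These are subjects short of day 365. Some will already have failed, so the count is an upper limit on those whose outcome can still change. It is not an estimate of bias.

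**The case against.** The sentence is a prohibition with an exception. A reader might infer that the SAP plans to release interim results at an enrolment stop. It does not say so: it permits sharing, and what is shared could be the decision alone.

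A reader might also infer that the two measures contradict each other. They can be read together: after a stop, sponsor staff outside the conduct team may be told, while conduct staff stay closed until filing is prepared. For sites there is a gap and no contradiction, because the second measure does not mention them.

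A third tempting reading is that Protocol 9.6 breaches the firewall. That is not shown. Section 9.6 concerns aggregate safety data, whereas the SAP bars summaries of endpoint data. Primary safety events are adjudicated by a committee, the review is not limited to those events or to the main study, and nothing says that the safety lead belongs to the conduct team. Protocol 9.5.1 gives the sponsor ongoing safety evaluation under the study safety management plan, and 9.6 says oversight follows the safety management plan. In a single-arm trial, pooled primary adverse events would come close to the primary safety result. The fair description is an overlap that the documents leave unreconciled.

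A share of 160 / 400 = 40% at the full 400 would be the wrong figure to cite: enrolment ends at the cap without any interim decision, so the exception need not come into play.

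The existing safeguards count. Core labs read the transtelephonic and Holter recordings, 12-lead tracings showing arrhythmia beyond 90 days are independently adjudicated, transmission frequency is fixed, and late antiarrhythmic use or oral amiodarone must come with documented arrhythmia. Most primary safety events fall within 7 days and are largely complete at a stop. These measures limit biased assessment. They do not reach the decision to cardiovert, re-ablate or prescribe.

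Finally, SAP sections 4-8, the protocol's statistics section and the monitoring committee charter are not available here and may hold release rules. The stopping criteria are not visible either, so it cannot be said that sites would learn the trial is predicted to succeed. This lowers the severity. The sentence in section 3 would still have to agree with any such rules.

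**Conclusion.** The point holds at moderate severity. As worded, SAP section 3 lets an enrolment stop alone open interim results to the sponsor and to sites, while up to a year of primary effectiveness follow-up remains in unmasked subjects. This is a stated rule that permits avoidable operational bias. The only visible later barrier covers sponsor conduct staff, leaves sites out, and uses a release time that is not aligned with the first.

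The illustrative size is about 160 main-study subjects short of day 365, or 53% to 80% of a trial stopped at 300 or 200, and more if the main study accrues faster. It rests on even accrual and assumed stopping sizes, and the effect on the endpoint is not quantified. The conclusion itself needs only the wording of section 3 and the planned year of follow-up. Protocol 9.6 is a secondary matter of clarification.

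**What to change.** Reword SAP section 3 as follows:

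1. At a decision to stop enrolment, only that decision (enrolment complete) goes to sites and to sponsor conduct personnel.
2. Numerical interim results are not released to them before the last main-study 12-month visit and database lock.
3. If a filing analysis is triggered earlier, it goes only to sponsor staff with no role in site contact, data review or adjudication.
4. The two existing measures are given one release time, sites are named in both, and the text is checked against any release rules in the SAP sections not visible here.

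In Protocol 9.6, state how the aggregate safety review sits with the firewall. One option is for safety staff outside the conduct team to do it. Trend review should stay: restricting the safety lead to single cases would defeat the section's purpose of picking up emerging problems promptly.

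The cost is an edit to both documents and later access to the numbers for the study team and sites. The independent statistician and the data monitoring committee are already in place.
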